2.3 REGISTRATION AND TREATMENT ASSIGNMENT PROCEDURES

2.3.1 Prior to Registration for this Protocol

Patients will initially sign the consent for and enroll on protocol 03-C-0277 prior to tumor harvest and leukapheresis for generation of the cell product. Patients will then sign the consent for and register for Part One of this treatment protocol. If the mRNA vaccine meets the requirements specified in the Certificate of Analysis (CoA) (**Appendix C**) to include USP <71> sterility testing, the vaccine will be released by Moderna and shipped to the NIH Clinical Center Pharmacy, where it will be dispensed and administered to the patient after receipt by the pharmacy of a physician's order. The patient must meet the eligibility criteria and be registered to Part Two of this treatment protocol before receiving the vaccine. If the mRNA vaccine does not meet the requirements specified in the CoA, the vaccine will not be released by Moderna and the patient will be taken off-study (Section **3.8.2**).

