2.3.2 Registration Procedure

Registration will be a two-part process. Authorized staff must register an eligible candidate with the NCI Central Registration Office (NCI-CRO) within 24 hours of signing consent. To initially register a subject after the participant has signed the consent, complete the top portion of the registration Eligibility Checklist from the website

(http://home.ccr.cancer.gov/intra/eligibility/welcome.htm) indicating that the patient is being registered for Part One and send via encrypted email to the NCI-CRO at [contact].

Once the mRNA vaccine meets the requirements specified in the CoA and the vaccine is released by Moderna, and eligibility is confirmed after completion of screening studies, authorized staff must complete the remainder of the eligibility checklist, indicating that the patient is being registered for Part Two (treatment on study). Email the completed registration Eligibility Checklist to the NCI-CRO at [contact].

After confirmation of eligibility at the NCI-CRO, CRO staff will call pharmacy to advise them of the acceptance of the patient on the protocol prior to the release of any investigational agents. Verification of registration will be forwarded electronically via email to the research team. A recorder is available during non-working hours.

Subjects that do not meet screening criteria should be removed from the study following the procedure in Section **3.8.3**.

Note: Patients are not considered to be fully enrolled on this treatment protocol unless they meet the eligibility criteria and are registered to Part Two.

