3.1.4 Dose-Limiting Toxicity

The dose-limiting toxicity (DLT) evaluation period for determination of the maximum tolerated vaccine dose (MTD) will occur during the 21 days after the first vaccination for each patient. A DLT is defined as follows: All grade 3 or greater toxicities related to the mRNA vaccine, with the exception of:

- Grade 3 fever
- Grade 3 pruritus/itching
- Grade 3 fatigue
- Grade 3 metabolic laboratory abnormalities without significant clinical sequela that resolve to grade 2 or less within 7 days.
- Grade 3 autoimmune toxicity that resolves to grade 2 or less within 7 days.
- Events that are clearly related to the patient's disease.
- 3.1.5 Phase I Dose Escalation

Subjects will receive their assigned dose level of NCI-4650 as IM injections on Days 0, 14, 28, and 42. The maximum dose of mRNA vaccine for each dose level will be:

Dose Level	vel NCI-4650, mRNA Vaccine Dose	
Level 1	0.04 mg (0.0006 mg/kg based on a 70-kg subject)	
Level 2	0.13 mg (0.0019 mg/kg based on a 70-kg subject)	
Level 3	0.39 mg (0.0056 mg/kg based on a 70-kg subject)	

Moderna is the sponsor of a dose escalation trial utilizing a nearly identical vaccine (mRNA-4157) as the mRNA vaccine used in this protocol (NCI-4650). The dose escalation in both protocols is the same (0.04 mg, 0.13 mg, and 0.39 mg). As indicated in the Moderna Safety Review Committee Dose Level Approval Form dated 21 December 2017, the Moderna Medical Monitor noted that for the three patients enrolled on Dose Level 1 (Part A) in the Moderna trial (0.04 mg mRNA-4157 monotherapy), no DLTs were experienced and the only AEs experienced were grade 1 injection site soreness, which is expected for the vaccine. As a result, Dose Level 1 was declared safe and tolerated. For this trial, because Dose Level 1 was shown to be safe and tolerated, the first two patients were enrolled on Dose Level 2. No DLTs were experienced and the only AEs experienced were grade 1 and 2 related events.

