3.2 PROTOCOL STOPPING RULES

New subject enrollment to the protocol will be temporarily halted if any of the following conditions are met, and consideration will be given to the need for protocol revisions regarding safety, if applicable. Consultation with the FDA may be arranged by the Sponsor before or after the protocol amendment is submitted to the NIH Intramural IRB, as needed.

- During the Phase I portion of the study If two DLTs, as described in Section **3.1.4**, occur at Dose Level 1.
- During the Phase II portion of the study Once five or more patients have been enrolled, if 20% or more patients cumulatively enrolled develop a DLT, as described in Section 3.1.4.
- During the Phase I and II portions of the study Any death that is at least possibly attributed to the investigational agent and which occurs within 30 days of receiving the investigational agent.

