required to perform the initial safety evaluation. In order to complete the dose escalation phase and Phase II, a total of up to 18+46 =64 patients may be required (allowing up to 2 inevaluable patients per Phase II cohort). Up to 6 patients enrolled at the MTD will count towards the accrual in the Phase II portion of the trial if they are evaluable for response and if they would be fully eligible for enrollment in the Phase II portion of the trial. Provided that about 2-3 patients per month will be able to be enrolled onto this trial, approximately 2-3 years may be needed to accrue the maximum number of required patients. However, as adequate responses to proceed to the second stage of accrual may not occur, the trial may end up accruing many fewer patients.

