8.3 POPULATIONS FOR ANALYSES

8.3.1 Evaluable for Toxicity

All patients will be evaluable for toxicity from the time of their first mRNA vaccine dose.

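### The Phase II safety halt counts patients not yet dosed or still under DLT observation as DLT-free, which modestly delays the halt; Section 3.2 should be reconciled with Sections 3.1.4 and 8.3.1

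*Combined protocol and SAP*

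**What the plan says.** Section 3.2 (Protocol Stopping Rules) opens: "New subject enrollment to the protocol will be temporarily halted if any of the following conditions are met". Its Phase II condition applies "Once five or more patients have been enrolled" and is met "if 20% or more patients cumulatively enrolled develop a DLT", with the DLT taken from Section 3.1.4.

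Three other sections determine what that ratio contains:

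- Section 3.1.4: the DLT evaluation period "will occur during the 21 days after the first vaccination for each patient".
- Sections 2.3.1 and 2.3.2: a patient must "be registered to Part Two of this treatment protocol before receiving the vaccine", and "Patients are not considered to be fully enrolled on this treatment protocol unless they meet the eligibility criteria and are registered to Part Two". Enrollment is therefore complete before the first dose.
- Section 8.3.1: "All patients will be evaluable for toxicity from the time of their first mRNA vaccine dose". The toxicity population starts at dosing, not at registration.

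No section limits the halt's denominator to dosed or fully observed patients, or makes Phase II enrollment wait for open observation periods. The dosing stagger in Section 1.2.9 is stated for the Phase I cohort. The plan gives no operating characteristics for the halt.

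**The concern.** The numerator can grow only after a patient has been vaccinated and followed. The denominator grows at registration. While accrual is running, the ratio therefore understates the DLT proportion among patients who have had the full chance to show one.

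The rule moves in whole DLTs, so a small dilution can matter. Just above each multiple of five, one pending patient raises the number of DLTs needed by one. At stake is how many further patients enter before the team pauses to consider revisions. A delay matters most early in Phase II, when a pause would spare the most patients.

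**Working it through.** **Inputs from the documents.** Limit 20% and start at five enrolled (3.2); 21-day period (3.1.4); up to 46 Phase II patients (8.2); accrual "Provided that about 2-3 patients per month will be able to be enrolled onto this trial" (8.2).

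**Assumptions, not in the documents.** True DLT rate 5% to 40%; lag from Part Two registration to first dose 0, 2 or 7 days; DLT times uniform over the 21 days; random arrivals.

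**Step 1. Patients pending at any time.** Expected number = monthly accrual × days / 30.4.

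- Inside the 21-day window: 2 × 21/30.4 = 1.4, and 3 × 21/30.4 = 2.1.
- Registered but undosed, 2-day lag: 2 × 2/30.4 = 0.13, and 3 × 2/30.4 = 0.20. With a 7-day lag at 3 per month: 3 × 7/30.4 = 0.69.

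Most of the dilution comes from patients under observation, not from undosed ones.

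**Step 2. DLTs needed.** Minimum = 0.20 × denominator, rounded up. As written this is 1 at 5 enrolled, 2 at 6, 3 at 11, 4 at 16 and 5 at 21. With one patient pending at 6, 11, 16 or 21 enrolled, the same limit applied to observed patients needs one DLT fewer.

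- 1/5 = 20.0% (halt); with one pending, 1/6 = 16.7% (no halt).
- 2/9 = 22.2% (halt); with two pending, 2/11 = 18.2% (no halt).

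Both examples depend on order. In the second, patients 10 and 11 must both be registered before the second DLT appears. If only ten are registered, 2/10 = 20% and the written rule fires.

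**Step 3. How often this changes the outcome.** There is no stated figure to reproduce, so the rule was simulated (3,000 trials per setting in the 0- and 7-day rows). Matched means DLTs divided by patients who have had a DLT or completed 21 days, with monitoring still starting at five enrolled.

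| Accrual, lag | True rate | Ever halts: written / matched | By 12th enrollee: written / matched |
|---|---|---|---|
| 2 per month, 0 days | 20% | 87% / 90% | 74% / 79% |
| 3 per month, 2 days | 20% | 85% / 90% | 69% / 79% |
| 3 per month, 7 days | 20% | 83% / 90% | 67% / 79% |
| 2 per month, 0 days | 30% | 99% / 99% | 89% / 91% |
| 3 per month, 7 days | 30% | 98% / 99% | 84% / 91% |
| 3 per month, 7 days | 40% | 100% / 100% | 95% / 98% |

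Monte Carlo error with 3,000 trials is under one point: √(0.85 × 0.15/3000) = 0.7 points.

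**Step 4. Cost at tolerable rates.** Temporary halts rise from about 20–22% to 27–30% at a true 5%, from about 43–46% to 53% at 10%, and from about 73–75% to 81–82% at 16.7%. Across lags of 0 to 7 days the 10% figures span 39–46% as written and 52–56% matched.

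**Step 5. Where monitoring starts.** At a true 30%, 3 per month and a 7-day lag, mean enrollment at the halt is 8.0 as written and 7.0 matched with five enrolled as the start. It is 8.6 if the start also moves to five resolved patients. Changing the start along with the denominator would lose the benefit.

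**The case against.** The strongest defense is that this is a choice, not an error. Section 3.2 names both its counts explicitly, and nothing in 3.1.4 forbids dividing by enrolled patients. The matched ratio has its own bias, upward, because a DLT counts at once while a DLT-free patient waits 21 days. In percentage points it adds more halts at tolerable rates than at high ones. DLTs in pending patients do reach the numerator later. The team reviews toxicity weekly (Section 7.6.1), and a possibly attributable death triggers a separate halt. All of this stands. It limits the size of the point and requires the cost to be stated. It does not explain why the halt should use a different set of patients from the toxicity population in 8.3.1.

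Four stronger readings might be inferred; the documents do not support them.

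- *The safeguard fails.* It does not: at true rates of 30% or more it still fires in about 98% of trials or more.
- *Patients waiting for vaccine manufacture dilute the rate.* They are in Part One only and are not counted as enrolled.
- *Many more patients are pending, because Phase II observation runs past 21 days.* Section 3.2 refers to 3.1.4, whose only stated period is 21 days.
- *Faster accrual clearly weakens the rule.* At a true 20% and a 2-day lag, the chance of ever halting as written is 85.2% at 2 per month and 85.4% at 3. Only the early chance falls: by the 12th enrollee with no lag, from 74% to 70%.

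**Conclusion.** The point holds as a modest defect in a safety rule. The numerator and denominator of the Phase II halt cover different patients, and the mismatch always pushes the ratio down. At the planned accrual the main consequence is delay: at a true 20% rate, roughly 5 to 12 percentage points fewer halts by the 12th enrollee (79 − 74 and 79 − 67), and 3 to 7 points fewer over the whole of Phase II (90 − 87 and 90 − 83).

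The fractions in Step 2 are exact. The simulated percentages rest on the assumed lag, DLT timing and true rates. They also assume continuous accrual to 46, without the pause of up to 6 months that Section 8.2 allows between stages; such a pause would let open windows clear and reduce the difference.

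**What to change.** Reconcile Section 3.2 with Sections 3.1.4 and 8.3.1 so that numerator and denominator cover the same patients, and say which patients those are. At a minimum the denominator should contain no undosed patients. By Step 1 that alone removes little of the dilution. The set that matches the numerator is patients who have completed the 21-day period or have had a DLT.

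State the five-enrolled start in its own clause, unchanged, so that monitoring does not begin later. Leave the 20% limit as it is. Report the number of patients still under observation beside the rate at each check. The same sentence could say whether Phase I patients, including those at the MTD carried into Phase II, count as cumulatively enrolled; the current text does not.

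The drafting cost is one sentence. The operating cost is the extra temporary halts in Step 4, which the protocol should acknowledge. Because the halt is temporary and leads to review, that cost is limited, and the count of pending patients helps the team interpret a halt that rests on few resolved patients.

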3.3 DRUG ADMINISTRATION

Patients will receive the mRNA vaccine on days 0, 14 (\pm 5 days), 28 (\pm 5 days), and 42 (\pm 5 days). The vaccine will be administered as an IM injection.

The patient's vaccine is delivered to the Patient Care Unit by the research nurse. Prior to the injection, the vaccine identity label is double-checked by two authorized staff (MD or RN), and an identification of the product and documentation of administration are entered in the patient's chart.

- The NCI-4650 mRNA vaccine will be administered as an outpatient procedure in the 3SE Day Hospital in the NIH Clinical Center.
- For all subjects, NCI-4650 will be administered by IM injection into the deltoid muscle (alternating deltoid muscle sites should be used for each subsequent injection, and injection sites may also be rotated to thigh muscles).
- The dose volume for Dose Levels 1 and 2 will be held constant at approximately 0.3 mL per injection. The dose volume for Dose Level 3 (PN 85002) will be at least 0.39 mL.
- The NCI Pharmacy Manual contains specific instructions for the preparation and administration of each dose level of NCI-4650.
- The NCI Pharmacy Manual contains details regarding sterility release of NCI-4650.

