lipid excipients: SM-102; 1,2-dimyristoyl-*rac*-glycero-3-methoxypolyethylene glycol-2000 (DMG-PEG 2000); 1,2-distearoyl-sn-glycero-3-phosphocholine (DSPC); and cholesterol. SM-102 is a novel, ionizable lipid that complexes with the mRNA component of NCI-4650 (mRNA product intermediate [MPI]) to promote the formation of the LNPs. The commercially-available lipids, DMG-PEG 2000, DSPC, and cholesterol, also contribute to the overall pharmaceutical properties of the LNPs.

NCI-4650 is provided as a sterile liquid for injection in a 93 mM Tris, 7% propylene glycol, 1 mM DTPA buffer, at a concentration of 1.0 mg RNA/mL.

Stability: Please refer to the NCI Pharmacy Manual.

Storage: NCI-4650 must be stored in a restricted access area under the storage conditions indicated on the product label and in the NCI Pharmacy Manual. Vials should be stored frozen at $-20^{\circ}C (\pm 5^{\circ}C) (-13^{\circ}F \text{ to } 5^{\circ}F)$.

How Supplied: NCI-4650 is supplied as solution for injection in 2-mL glass vials (with a septum stopper). Each vial contains 0.6 mL.

Preparation: The dose volume for Dose Levels 1 and 2 will be held constant at approximately 0.3 mL per injection. The dose volume for Dose Level 3 (PN 85002) will be at least 0.39 mL. The NCI Pharmacy Manual contains specific instructions for the preparation and administration of each dose level of NCI-4650. The NCI Pharmacy Manual also contains details regarding sterility release of NCI-4650.

Administration: For all subjects, NCI-4650 will be administered by IM injection into the deltoid muscle (alternating deltoid muscle sites should be used for each subsequent injection, and injection sites may also be rotated to thigh muscles).

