13.3 APPENDIX C: MRNA-4650 CERTIFICATE OF ANALYSIS

moderna

[name] [contact] • [contact]

CERTIFICATE OF ANALYSIS

Product Description: mRNA-4650 Labeled Drug Product

Manufacturer Name: Moderna

Manufacturer Lot #: 85002xxxyy

Moderna Lot #: 85002xxxyy

Date of Manufacture: DDMMMYYYY

Expiry Date: DDMMMYYYY

Product Specification #: SPC-0380

Moderna Part #: 85002

Container/Closure: 2R Vial, 13mm Stopper, 13mm Flip Cap

Result

Product	Method	
Attribute	(Test Method #/Revision #)	

Specification

Source Data

		mRNA-4650 mRNA Product Intermediate (MPI)	
Residual DNA template	qPCR Moderna SOP-0491	< 1% (w/w)	ARN 18- 00175-034
Residual total protein	Fluorescence (NanoOrange) Moderna SOP-0521	< 1% (w/w)	ARN 18- 00175-035
% 5' Capped	RP-HPLC Moderna SOP-0467	≥85% Cap1	ARN 18- 00258-023
% Poly A Tailed RNA (% Tailless RNA)	RP-HPLC Moderna SOP-0291	Report % area main peak (Report % area pre-main peak)	ARN 18- 00258-038
		mRNA-4650 Drug Product – Final Vial	
Appearance	Visual Moderna SOP-0278	White to off-white dispersion. May contain visible, white or translucent product-related particulates	ARN 18- 00258-045
Total RNA content	AEX-HPLC Moderna SOP-0235	0.8 – 1.2 (mg/mL)	ARN 18- 00258-026
Identity	Reverse Transcription Sanger Sequencing Moderna SOP-0492	Sequence matches 100% description of the patient-specific coding region	ARN 18- 00175-038
Purity	RP-HPLC Moderna SOP-0383	≥ 50% sum of main peak areas	ARN 18- 00258-029
Product- related Impurities	RP-HPLC Moderna SOP-0383	Report % Area for each impurity group Impurity Group 1 (pre-main peak 1) Impurity Group 2 (post-main peak 2) Impurity Group 3 (mRNA-adduct species)	ARN 18- 00258-029
% RNA Encapsulation	Fluorescence (Ribogreen) Moderna SOP-0298	≥ 80%	ARN 18- 00258-042
pH	USP <791> Moderna SOP-0288	7.0-8.0	ARN 18- 00258-044

CONFIDENTIAL-DO NOT DISTRIBUTE OUTSIDE OF MODERNA, INC. WITHOUT WRITTEN PERMISSION

VERSION NUMBER 1.0

Page 1 of 3

Ē

moderna

[name] [contact] • [contact]

		CERTIFICATE O	F ANALYSIS		
Product Description: mRNA-4650 Labeled Drug Product		Moderna Part #: 85002			
Manufacturer Name: Moderna			Container/Closur	e: 2R Vial, 13mm Stopper	r, 13mm Flip Cap
Manufacturer L	ot #: 85002xxxyy				
Moderna Lot #:	85002xxxyy	Product Specification #: SPC-0380			
Date of Manufacture: DDMMMYYYY			Expiry Date: DDMMMYYYY		
Product Attribute	Method (Test Method #/Revision #)	Specificatio	n	Result	Source Data

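### Do the 0.39 mg maximum and the 0.39 mL minimum volume for Dose Level 3 contradict each other?

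*Combined protocol and SAP*

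**What the plan says.** Section 3.1.5 introduces the dose table with "The maximum dose of mRNA vaccine for each dose level will be" and gives 0.39 mg for Level 3. Section 3.1.6 treats the same 0.39 mg as the highest planned clinical dose and rests the roughly 9-fold rat safety margin on it.

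Section 3.3 gives the volumes. For the two lower levels: "The dose volume for Dose Levels 1 and 2 will be held constant at approximately 0.3 mL per injection". For the third: "The dose volume for Dose Level 3 (PN 85002) will be at least 0.39 mL". Section 11.2.1 repeats both sentences. No upper volume is given for Level 3.

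Section 11.2.1 supplies the product "at a concentration of 1.0 mg RNA/mL" in vials of 0.6 mL. The certificate in Appendix C is headed "Moderna Part #: 85002", the part number named in the Level 3 volume sentence, and its release range for total RNA content is 0.8 to 1.2 mg/mL. Lots are individual to each patient; the identity test reads "Sequence matches 100% description of the patient-specific coding region".

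On preparation, Section 3.3 says: "The NCI Pharmacy Manual contains specific instructions for the preparation and administration of each dose level of NCI-4650". Section 11.2.1 says the same. The Manual is not among the documents available for this review.

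**The concern.** A ceiling in milligrams and a floor in millilitres are linked only by concentration, and concentration may vary by 20% either side of nominal. Read as undiluted injection, any lot stronger than 1.0 mg/mL would exceed the stated maximum at every volume that meets the floor. The protocol body does not say whether Level 3 is diluted, whether volume is adjusted to the measured lot strength, or which limit governs if they differ.

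Level 3 matters. It is the level being enrolled under Section 3.1.5. If no dose-limiting toxicity (DLT) is seen at any level, it becomes the maximum tolerated dose (MTD) by definition and, under Section 3.1.7, the Phase II dose. Sections 8.4.2 and 8.4.4 report toxicity by dose level, so a reader would want to know that the label stands for a reasonably uniform delivered mass.

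**Working it through.** **Inputs.** Level 3 maximum 0.39 mg (3.1.5); Level 3 volume at least 0.39 mL (3.3, 11.2.1); Levels 1 and 2, 0.04 and 0.13 mg in about 0.3 mL (3.1.5, 3.3); nominal strength 1.0 mg/mL and vial fill 0.6 mL (11.2.1); release range 0.8 to 1.2 mg/mL (Appendix C); human equivalent of the highest rat dose 3.51 mg (3.1.6).

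**Step 1: reproduce the plan's figures at nominal strength.** Dose = volume x strength.
- 0.39 mL x 1.0 mg/mL = 0.39 mg, the stated dose.
- 0.39 / 70 = 0.00557 mg/kg, stated as 0.0056.
- 3.51 / 0.39 = 9.0-fold, the stated margin.

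**Step 2: vary lot strength, assuming undiluted product.**

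| Lot strength (mg/mL) | Mass in 0.39 mL (mg) | Against 0.39 mg | Volume holding 0.39 mg (mL) |
|---|---|---|---|
| 0.8 | 0.312 | -20% | 0.4875 |
| 0.9 | 0.351 | -10% | 0.4333 |
| 1.0 | 0.390 | 0% | 0.3900 |
| 1.1 | 0.429 | +10% | 0.3545 |
| 1.2 | 0.468 | +20% | 0.3250 |

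For lots at or below 1.0 mg/mL, the volume holding 0.39 mg is at or above the floor and within one 0.6 mL vial, so both limits can be met. Only the rows above 1.0 mg/mL clash. The extreme spread within Level 3 is 0.468 / 0.312 = 1.5-fold.

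**Step 3: is undiluted use what the text implies?** For the lower levels, 0.04 / 0.3 = 0.13 mg/mL and 0.13 / 0.3 = 0.43 mg/mL. Both are well below 1.0 mg/mL, so dose volume there must mean a final, diluted volume. The next sentence uses the same term for Level 3. Level 3 could not fit the 0.3 mL volume at nominal strength, since 0.3 x 1.0 = 0.30 mg, which explains why it has its own volume sentence.

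**Step 4: can both limits be met for a strong lot?** Arithmetically, yes. At 1.2 mg/mL, 0.325 mL of product plus 0.065 mL of diluent is 0.39 mL holding 0.39 mg. This shows only that the two sentences are compatible; it is not a proposal for preparation.

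**Step 5: consequence in the worst case.** With Level 2 20% high and Level 3 20% low, 0.13 x 1.2 = 0.156 mg against 0.39 x 0.8 = 0.312 mg, still 2.0-fold apart. At 0.468 mg the rat margin is 3.51 / 0.468 = 7.5-fold.

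**The case for a change.** The strongest case for a change is that the protocol uses the word maximum, not nominal or target. If 0.39 mg is taken as a nominal dose at nominal strength, the words at least are unexplained, because any undiluted volume above 0.39 mL then exceeds 0.39 mg. Dilution at Level 3 is written nowhere, and at Levels 1 and 2 it is only inferred. Section 7.1.8 defines a deviation as a departure from the approved protocol, and Section 7.2.1 requires all deviations to be reported within 7 days, so whether an injection of, say, 0.43 mg is reportable turns on protocol wording. One reconciling sentence would be cheap.

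Part of this stands. The protocol body does leave the handling of lot strength unstated, and the part number ties the release range to Level 3. But the floor wording has a natural reading as an allowance for weaker lots, which need more than 0.39 mL to hold 0.39 mg, or as a final volume after dilution. The mass maximum itself limits how much product may be drawn, so the missing volume ceiling is less open than it looks. Dilution and lot adjustment are preparation matters, which the protocol assigns to the Manual; their absence from the protocol body does not show that they are absent from the trial.

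A derived delivered-mass variable has also been suggested. The certificate provides for an RNA content result for each lot, and Section 3.3 already requires administration to be documented in the chart. Such a variable could be built later if wanted, but no decision rule would use it.

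**Conclusion.** No change to the plan follows. The stated figures reproduce exactly at nominal strength. The two limits are incompatible only under two conditions together: undiluted injection, which the text does not state and the lower dose levels argue against, and a lot above 1.0 mg/mL. Even then, the excess at the minimum volume is at most 20% (0.468 against 0.39 mg), with the dose levels still ordered and at least two-fold apart.

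The statistical conclusions are not exposed. DLTs are counted by assigned level, the MTD rule in Section 3.1.5 uses those counts, and the Phase II two-stage design uses response counts; none takes delivered mass as an input. A sponsor who follows the stated maximum, the stated minimum volume and the Manual obtains the same DLT, MTD and Phase II conclusions.

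This rests on the Manual containing the preparation instructions that Sections 3.3 and 11.2.1 say it does, which could not be checked here. It also uses only the part of the certificate that was available, and no lot data are given, so the 20% figures are specification limits rather than observed values. If the Manual turned out to be silent, the sponsor would have to reconcile Sections 3.1.5, 3.3 and 11.2.1 and Appendix C; which limit governs would be for the sponsor to decide.
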